4.2 INCLUSION CRITERIA

1. Females, 18 to 45 years of age.
2. Previously confirmed diagnosis of PCOS by Rotterdam criteria¹⁷ (at least 2 of 3):
 - 1) oligo-and/or anovulation;
 - 2) hyperandrogenism (clinical and/or biochemical);
 - 3) polycystic ovary morphology on ultrasonography (either 12 or more follicles measuring 2–9 mm in diameter or an increased ovarian volume >10 cm³).
3. Evidence of NAFLD within 6 months prior to the Screening Visit (Visit 1). The diagnosis of NAFLD is made according to the American Association for the Study of Liver Diseases criteria.¹⁸
 - a) hepatic steatosis by imaging or histology,
 - b) no significant alcohol consumption,
 - c) no competing etiologies for hepatic steatosis, and
 - d) no co-existing causes for chronic liver disease.
4. Alanine transaminase ≥ 38 U/L at Visit 1. Visit 2 ALT must not increase $>30\%$ from Visit 1.
5. Hepatic fat fraction $\geq 10\%$ by MRI-PDFF.
6. Willingness to participate in the study.
7. Ability to understand and give informed consent for participation.
8. A normal pelvic examination within past 6 months before randomization.
9. A normal breast examination at screening (If Mammogram has been done in the preceding 12 months it will be documented. If patient is not up to date with standard breast cancer screening guidelines and is willing to receive screening, mammogram

 Zydus Discovery DMCC	CLINICAL TRIAL PROTOCOL Saroglitazar Magnesium – Phase 2A SARO.17.009	Confidential Page 40 of 82
--	---	-------------------------------

will be offered prior to enrollment as part of standard care).

10. A normal Papanicolaou (PAP) test within past 6 months before randomization (If PAP test has not been performed within 6 months of the screening visit, it must be performed during screening).
11. Woman who agrees to use the following contraceptive methods:
 - a. Combination hormonal contraceptives (including pills, patches and vaginal rings). For the following conditions, the usage of the combination hormonal contraceptives should be based upon a discussion with the subject and the investigators' clinical judgment.
 - i. Women greater than 35 years of age who also smoke fewer than 15 cigarettes per day
 - ii. Adequately controlled hypertension
 - iii. Properly taken blood pressure above a systolic 140-159 mm Hg or diastolic 90-99 mm Hg
 - iv. Known hyperlipidemia
 - v. Diabetes associated with vascular disease, including neuropathy, retinopathy and nephropathy.

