 - vi. Diabetes duration greater than 20 years.
 - b. Women with the following conditions should use effective methods other than combined hormonal contraceptives (e.g., Progestogen-only oral contraceptives or progestogen-containing intrauterine devices (IUD), Non-hormonal IUD, Double-barrier contraception [e.g., condom plus diaphragm]):
 - i. Women greater than 35 years of age who also smoke 15 or more cigarettes per day
 - ii. Properly taken blood pressure above systolic \geq 160 mm Hg or diastolic \geq 100 mm Hg
 - iii. Known hyperlipidemia
 - iv. Vascular disease, including neuropathy, retinopathy and nephropathy
 - v. Diabetes duration greater than 20 years.

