5.8 CONCOMITANT THERAPY

All medications received by the subject at any time prior to the Screening Visit and taken within 3 months before the Screening Visit, during the interval between the Screening Period and Randomization and those taken throughout the trial will be recorded on the appropriate section of the eCRF. The site may rely on subject reports for this information. All subjects must be questioned about concomitant medication at each visit. All concomitant medication, both prescribed and over-the-counter, must be recorded in the eCRF. This includes drugs used on a chronic and as needed basis. Medications that are indicated as prohibited in the Exclusion Criteria must not be used after the Screening Visit during the interval between the screening period and randomization or during the trial.

The following treatment/drugs will be allowed during the study.

- Treatment for common illness during the study may be allowed.

Approved by: [name]	Protocol No. SARO.17.009 Version No.: 5.0
------------------------------------	--

 Zydus Discovery DMCC	CLINICAL TRIAL PROTOCOL Saroglitazar Magnesium – Phase 2A SARO.17.009	Confidential Page 50 of 82
---	---	-------------------------------

- Stable antidiabetic and lipid lowering medications at least for the 3 months preceding screening.
- Stable doses of metformin or any treatment of PCOS at least for the 3 months preceding screening.
- For any required concomitant medication, the patient must be on a stable dose for 3 months at study entry and patients must continue with their current drug regimen without any change in dosage.

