6.1.2 Secondary Endpoints

1. Changes from baseline to Week 12 and Week 24 in liver enzymes/LFTs: ALT, AST, ALP, GGT, serum protein, albumin and total bilirubin.
2. Changes from baseline to Week 12 and Week 24 in insulin resistance as measured by HOMA.
3. Changes from baseline to Week 24 in markers of liver injury and fibrosis including CK-18, hs-CRP, TNF α , and liver stiffness measured by transient elastography/FibroScan[®].
4. Changes from baseline to Week 24 in controlled attenuation parameter measured by transient elastography/ FibroScan[®].
5. Changes from baseline to Week 12 and Week 24 in body weight, BMI and in waist circumference.
6. Changes from baseline to Week 24 in MRI-derived measures of total liver fat index and total liver volume.
7. Changes from baseline to Week 12 and Week 24 in lipid and lipoprotein levels: TG, TC, HDL, LDL, sdLDL, VLDL, apolipoprotein A and apolipoprotein B.
8. Changes from baseline to Week 12 and Week 24 in SHBG level.
9. Changes from baseline to Week 12 and Week 24 in ovarian function (Total testosterone, 17-hydroxyprogesterone, free testosterone, luteinizing hormone, follicle-stimulating hormone, LH-to-FSH ratio and estradiol).
10. Changes from baseline to Week 12 and Week 24 in free androgen index.
11. Pharmacokinetics of Saroglitazar following first dose and last dose.

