Note: Efficacy assessments and laboratory assessment (liver fat content by MRI-PDFF [MRI-PDFF will be performed during screening phase, screening phase results will be used as the baseline assessment], controlled attenuation parameter, hormonal profile, fasting plasma glucose, lipid and lipoprotein profiles, MRI-derived total liver fat index and total liver volume [MRI derived total liver fat index and total liver volume assessment will be performed during screening phase, screening phase results will be used as the baseline assessment], plasma insulin levels, homeostasis model assessment -insulin resistance [HOMA-IR], liver stiffness by transient elastography/FibroScan®, ovarian function, liver enzymes/LFTs, hematology, coagulation test (PT/INR), renal function test, CK, hs-CRP, BNP , NT-proBNP, cardiac troponin, CK-MB, lipase and amylase, TNFa, uric acid, TSH, T3 and T4, serology, HIV type 1 and type 2, HAV, antiHBsAg, HCV, serum pregnancy test, urine microscopy and urine chemistry) which will be done at Visit 1 will be considered for baseline visit. PAP test, endometrial biopsy and mammography will be performed as per Time and Events Schedule (refer **Appendix 1**).

Document Title:	Statistical Analysis Plan		
Version Number:	Final 1.0	Date:	18Oct2024
Protocol Number:	SARO.17.009	Sponsor Name:	Zydus Therapeutics INC

7 Study Design

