9.7.2.2 Analysis Strategy

The analysis for the secondary efficacy endpoints performed as below:

For the analysis of the secondary endpoints, i.e., Change from baseline in Liver Enzymes/LFTs, Insulin resistance (IR) measured by HOMA, CK-18, hs-CRP, TNF α , liver stiffness, controlled attenuation parameter, body weight, body mass index (BMI), waist circumference, total liver fat index, total liver volume, serum lipid profile and lipoproteins, sex hormone binding globulin level, ovarian function parameters and free androgen index. The analysis of covariance ANCOVA model will be applied separately at each visit as appropriate. The model will include treatment as a fixed effect and the corresponding baseline values of the endpoint as a covariate.

For each visits the estimate of the LS Means for treatment groups and its 95% confidence interval, LS Mean for treatment group difference (Saroglitzaz magnesium 4 mg – Placebo) and its 95% confidence interval of the LS Mean for treatment group difference, and p-value to check the significance difference at 5% level of significance will be generated from ANCOVA model. These analyses will provide the treatment effect at each visit while controlling for baseline differences

Descriptive summaries will be provided for all the secondary efficacy endpoints at each scheduled visit by treatment group. All secondary efficacy analysis will be conducted primarily based on the PP population and analysis, based on mITT population will be considered as supportive analyses .

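### The ANCOVA for the hormone endpoints ignores hormonal contraception, and the protocol does not clearly bar starting or changing it after the Visit 1 baseline

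*Protocol*

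**What the plan says.** **Contraception.** Protocol 4.2, criterion 11, enrols a "Woman who agrees to use the following contraceptive methods". Part (a) is "Combination hormonal contraceptives (including pills, patches and vaginal rings"). Part (b) reads "Women with the following conditions should use effective methods other than combined hormonal contraceptives" and gives progestogen-only, non-hormonal IUD and double-barrier methods as examples. The criterion gives no start date and no minimum prior use.

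**Stability.** Protocol 5.8 allows "Stable doses of metformin or any treatment of PCOS at least for the 3 months preceding screening". It adds: "For any required concomitant medication, the patient must be on a stable dose for 3 months at study entry", with no dosage change afterwards. Protocol 5.8.3.1 repeats the 3-month rule for permitted drugs, citing lipid-lowering and glycemic agents, but asks for an unchanged regimen only as far as possible. None of these sentences names contraceptives or refers to criterion 11.

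**Endpoints and baseline.** Protocol 6.1.2 includes "Changes from baseline to Week 12 and Week 24 in SHBG level" (endpoint 8), the ovarian-function parameters (9) and free androgen index (10). The note in SAP 6.3 lists the hormonal profile among the assessments "which will be done at Visit 1 will be considered for baseline visit". SAP 8.3 takes the latest value before first dose, but the text of SAP 9.8.2 places these assays at Screening, Week 12 and Week 24 only, so the hormone baseline is in effect Visit 1.

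**Analysis.** SAP 9.7.2.2: "The model will include treatment as a fixed effect and the corresponding baseline values of the endpoint as a covariate". The subgroups in SAP 9.9 are ALT and country, and no hormone endpoint is listed for them. Concomitant medications are only tabulated and listed (SAP 9.5).

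**The concern.** Objectives 8 to 10 ask whether the drug changes the same hormones that hormonal contraception is expected to change. That expectation is general pharmacology; the documents do not state it. Two kinds of participant matter.

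- A woman stably on a combined method may have little room for an ovarian response. If so, she dilutes the average drug effect on LH, FSH, estradiol and testosterone.
- A woman who starts a hormonal method after the Visit 1 draw has a baseline off the method and follow-up values on it. Her change then carries a contraceptive effect that the model treats as noise.

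The analysis set does not remove the second woman. SAP 8.2 excludes from the per-protocol set only participants with deviations that could affect the primary outcome, which is MRI-PDFF. A change that disturbs hormones alone need not exclude her, and that set is the main one for secondary endpoints. The trial is also small: SAP 7.3 closes recruitment at 60.

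**Working it through.** **Plan figures.** The documents give no sample size, power, SD or effect for any hormone endpoint. The calculation in protocol 8.6 concerns MRI-PDFF only and is not an input here.

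**From the documents.** 60 participants, 1:1, so 60/2 = 30 per arm (24 after 20% dropout: 30 × 0.8); model = treatment + baseline; two-sided 5%.

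**Assumed, not in the documents.** Correlation of baseline with follow-up 0.5; true drug effect 0.65 SD; a share *p* of women (0–50%) start a hormonal method after Visit 1, independently of arm; starting shifts the hormone by *s* = 1–3 SD.

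**Step 1: formula.** With no starters, the ANCOVA residual variance is 1 − 0.5² = 0.75. An unmodelled start adds s²p(1 − p). So

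residual variance = 0.75 + s²p(1 − p), and SE = √(2 × residual variance / 30).

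Examples:
- p = 0.25, s = 2: 0.75 + 4 × 0.1875 = 1.50, twice the variance; SE rises from 0.224 to 0.316.
- p = 0.5, s = 3: 0.75 + 9 × 0.25 = 3.00, four times the variance; SE 0.447.

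**Step 2: simulation of the planned ANCOVA** (20,000 trials per row, 30 per arm). The last column adds an indicator that identifies every starter.

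| Starters | Shift (SD) | Residual variance | Power as planned | Power with covariate |
|---|---|---|---|---|
| 0% | – | 0.75 | 0.81 | 0.81 |
| 10% | 1 | 0.84 | 0.77 | 0.81 |
| 10% | 2 | 1.11 | 0.64 | 0.80 |
| 25% | 1 | 0.94 | 0.72 | 0.81 |
| 25% | 2 | 1.50 | 0.51 | 0.80 |
| 50% | 1 | 1.00 | 0.69 | 0.80 |
| 50% | 2 | 1.75 | 0.45 | 0.80 |
| 50% | 3 | 3.00 | 0.29 | 0.80 |

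A t-test using the Step 1 variances agrees to within about 0.015. At 24 per arm the planned power runs from 0.71 (no starters) down to 0.24, and the covariate restores about 0.70.

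**Step 3: bias and false positives.** With no true effect, the mean error of the planned ANCOVA stays within 0.004 SD and its type I error is 0.047–0.053 over all scenarios (24, 30 and 37 per arm).

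**Step 4: chance imbalance.** The 95% range for the arm difference in the share of starters is ±1.96√(2p(1 − p)/30): ±22 percentage points at p = 0.25 and ±25 at p = 0.5. This is the mechanism behind the larger SE in Step 1, not an extra error on top of it.

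**Step 5: dilution.** If hormonal users show no drug effect at all (assumption), the average effect is 0.65(1 − f), where f is the share of users. For f = 25%, 50% and 75% it is 0.49, 0.33 and 0.16 SD, and power falls from 0.82 to 0.57, 0.30 and 0.11. A covariate does not repair this.

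**The case against.** **The stability rules may already settle it.** If contraceptives count as required medication or as PCOS treatment, protocol 5.8 bars a start after Visit 1. A reader might infer that the protocol permits late starts; it does not say so. It is silent on whether the rule applies, while a criterion based on agreement leaves a new start open. What stands is an ambiguity, not a licence. Stability would also not remove the dilution in Step 5.

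**Randomisation protects the contrast.** A reader might infer that objectives 8 to 10 cannot be answered, or that a chance excess of starters in one arm would pass for a drug effect. Step 3 shows otherwise when starting is unrelated to arm: that imbalance is ordinary sampling error, already in the ANCOVA standard error, and false positives stay near 5%. Bias would need starts or changes that differ by arm, or selection into the per-protocol set; nothing in the documents shows either.

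**The size comes from the inputs.** This stands. The documents give no contraceptive prevalence, and criterion 11(b) sends some women to other methods, including non-hormonal ones. An alternative set of assumptions for SHBG (24 per arm, residual SD 10 nmol/L, effect 9, rise 60–100) gives about 86% power with no starters and 10–33% with 10–30% starters. Those rises are 6 to 10 residual SDs; with 10% starters and rises of 1–2 SD, power is 0.72–0.81. No single figure should be quoted as the loss.

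**These are unpowered secondary endpoints in a proof-of-concept trial.** True, and the primary endpoint is not shown to be affected. That limits the weight of the point, but the remedy is cheap.

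**Conclusion.** The point holds as a loss of information on secondary endpoints 8 to 10, not as bias. The plan brings hormonal contraception into the trial, does not say clearly whether it must be stable before the Visit 1 draw, and leaves it out of every hormone analysis. In the scenarios examined, planned power drops from about 0.81 to between 0.77 and 0.29, depending on how many women start and how far the hormone moves. Recovery to about 0.80 is the favourable case: it assumes the covariate identifies every starter, all before randomisation, and that the shift is the same in each. In the alternative SHBG assumptions, where the rise varies between women, the covariate brings power back only to 38–76%.

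Two limits on interpretation follow. A null ovarian-function result would be hard to read if many women use combined methods. A change from baseline within one arm cannot be attributed to the drug.

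**What to change.** Amend SAP 9.7.2.2 before unblinding, for SHBG, free androgen index and the ovarian-function parameters:

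1. Add to the ANCOVA (a) hormonal-contraceptive class at randomisation (combined hormonal, progestogen-only, none; collapse if sparse) and (b) an indicator for a start or stop between the Visit 1 draw and Day 1. Both are fixed before randomisation, so they are valid covariates. Derive them from the medication record, which protocol 5.8.2 runs from 3 months before Visit 1. Barrier methods and non-hormonal IUDs may not be recorded there, so define the last class as no hormonal method recorded.
2. As supportive analyses only, repeat in women not on combined hormonal contraception at randomisation, and in women with no start or change of hormonal contraception after Visit 1. The first subset is not a random sample, because criterion 11(b) selects on smoking, blood pressure, hyperlipidemia and vascular disease, so the main ovarian-function conclusion should not rest on it. The second can depend on behaviour after randomisation.
3. Criterion 11 and the stability sentences in protocol 5.8 and 5.8.3.1 must be reconciled. So must parts (a) and (b) of criterion 11, which both list known hyperlipidemia and diabetes of more than 20 years. This review takes no position on which contraception rule should apply.

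**Cost.** SAP wording, two derived variables, and 1–3 degrees of freedom (2 for a three-level class plus 1 for the indicator; fewer if collapsed). Starts after Day 1 are addressed only by the supportive analysis. The subsets are small: at an assumed 50% use of combined methods, the first leaves about 15 of 30 per arm, or 12 of 24.

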4.3 EXCLUSION CRITERIA

1. Presence of other chronic liver diseases (hepatitis B or C, autoimmune hepatitis, cholestatic liver disease, Wilsons disease, hemochromatosis, etc.).
2. Average alcohol consumption \geq 7 drinks per week for women in the 6 months prior to enrollment. Subjects will be required to have an "Alcohol Use Disorder Identification Test" (AUDIT) score of <8 .
3. Clinical, imaging, or histological evidence of cirrhosis.
4. Any of the following laboratory values:
 - a. Hemoglobin <10 g/dL
 - b. White blood cell count $<4 \times 10^9$ /L
 - c. Neutrophil count $<1.5 \times 10^3$ / μ L
 - d. Abnormal baseline platelet counts ($<150 \times 10^3$ uL).

 Zydus Discovery DMCC	CLINICAL TRIAL PROTOCOL Saroglitazar Magnesium – Phase 2A SARO.17.009	Confidential Page 41 of 82
--	---	-------------------------------

- e. Total Serum bilirubin greater than the ULN (>1.3 mg/dL) (except in patient with known Gilbert Syndrome where TB up to 2.5 mg/dL is allowed)
- f. Albumin <3.2 g/dL
- g. Serum ALT or AST >250 IU/L
- h. Lipase or amylase more than the ULN at baseline.
- i. Serum creatinine ≥1.5 mg/dL
- j. Renal impairment as demonstrated by baseline estimated glomerular filtration rate (eGFR) < 60 mL/min/1.73 m² (calculated using the CKD-EPI equation).
- k. Total creatine kinase level more than the ULN at baseline.
- 5. Patient with INR >1.3
- 6. Patients who have used medications known to cause hepatic steatosis (e.g., corticosteroids, amiodarone, methotrexate, tetracycline, tamoxifen, anabolic steroids, or valproic acid) for more than 2 weeks in the past year.
- 7. Prior bariatric surgery.
- 8. Weight loss of more than 5% in the 3 months preceding screening.
- 9. Severe co-morbidities (e.g., advanced cardiac, renal, pulmonary, or psychiatric illness).
- 10. Known allergy, sensitivity or intolerance to Saroglitazar Magnesium, comparator or formulation ingredients (Saroglitazar Magnesium Micronized, Magnesium Oxide Light, Microcrystalline Cellulose, Anhydrous Lactose, Croscarmellose Sodium, Povidone k 30, Talc (luzena c), Colloidal Silicon Dioxide and Magnesium Stearate).
- 11. Use of antidiabetic and lipid lowering medications if the dose is not stable for at least the 3 months preceding screening.
- 12. Intake of Vitamin E (>100 IU/day) or multivitamins containing Vitamin E (>100 IU/day) 3 months before enrollment.
- 13. Use of drugs with potential effect on NAFLD/NASH such as S-adenosylmethionine (SAM-e), Betaine, Pentoxifylline, Thiazolidinediones (Pioglitazone, Rosiglitazone), Obeticholic Acid or Milk Thistle in the 3 months prior to screening.
- 14. Changing doses of statins (Simvastatin, Pravastatin, Atorvastatin, Fluvastatin, Lovastatin, Rosuvastatin) or Fibrates (Clofibrate, Fenofibrate) in the 3 months prior to enrollment.
- 15. Illicit substance abuse within the past 12 months.
- 16. Pregnant or breast-feeding females.
- 17. Poorly controlled diabetes with HbA1c $>8.5\%$
- 18. Use of total parenteral nutrition in the 6 months preceding enrollment.
- 19. Women with known Cushing syndrome or hyperprolactinemia.
- 20. Late onset congenital adrenal hyperplasia, androgen-producing tumors.
- 21. Refusal or inability to comply with the requirements of the protocol, for any reason, including scheduled clinic visits and laboratory tests.
- 22. History of myopathies or evidence of active muscle diseases.
- 23. History or current significant cardiovascular disease, including:
 - i. Unstable angina (i.e., new or worsening symptoms of coronary heart disease within the past 3 months before screening), acute coronary syndrome within the past 6 months before screening, acute myocardial infarction in the past 3 months or heart

 Zydus Discovery DMCC	CLINICAL TRIAL PROTOCOL Saroglitazar Magnesium – Phase 2A SARO.17.009	Confidential Page 42 of 82
--	---	-------------------------------

failure of New York Heart Association class (III-IV) or worsening congestive heart failure, or coronary artery intervention, within the past 6 months before screening.

- ii. History or current unstable cardiac dysrhythmias within prior 3 months before screening.
- iii. Uncontrolled hypertension (systolic blood pressure > 160 mmHg and/or diastolic blood pressure > 100 mmHg).
- iv. Stroke or transient ischemic attack prior 6 months before screening visit.

24. History of malignancy in the past 5 years and/or active neoplasm with the exception of resolved superficial nonmelanoma skin cancer.

25. History of bladder disease other than urinary tract infection or cystitis. Previous or current hematuria due to etiologies other than urinary tract infection or kidney stones.

4.3.1 Screen Failures

Patients who fail the screening criteria will not be rescreened unless approved by the Sponsor or its designee. Screening laboratory tests may be repeated following the approval of Sponsor or its designee if the laboratory test results seem implausible or inaccurate.

A screen failure occurs when a patient who has signed the informed consent form (ICF) does not meet all the entry criteria outlined in this protocol and has not been randomized or received study drug. No study procedures (including end-of-treatment procedures) will be performed for these patients. For patients who fail to meet the inclusion criteria or who meet 1 or more of the exclusion criteria, the Principal Investigator (PI) (or designee) will document on a screening log the reason for the screening failure.

